## Main variables

All-cause dementia [diagcog\_nt4eld\_dem] dichotom  
Primary outcome.

Hearing threshold level [nt2htl54best] continuous  
Primary exposure. The mean of the frequencies 0.5, 1, 2 and 4 kHz on the best ear measured in dB with automatic pure tone audiometry (PTA).

## Variables with missing information

Alcohol use [alcfmy\_nt2blq1] categorical covariate (604 missing)

- «How often do you drink alcohol?».
- 0 «Never»
- 1 «1-7 times/month»
- 2 «8-18 times/month»
- 3 «19-31 times/month»

(604 missing after 794 is replaced by «never drink»-answer [alcnev\_nt2blq1]).

Physical activity [parangul\_nt2] continuous mediator (480 missing)

- The index is the sum of the score for low and vigorous PA:

Low physical activity? (Not out of breath/sweat)	Hours/week	Scores
None	0	0
Less than 1 hour	0,5	0
1-2 hour	1,5	0,5
3 hours or more	3	1
Vigorous physical activity? (Out of breath/sweat)	Hours/week	Scores
None	0	0
Less than 1 hour	0,5	0,5
1-2 hour	1,5	1,5
3 hours or more	3	3

History of stroke [apoplev\_nt2blq1] dichotomous mediator (3 missing)

- «Have you ever had stroke/bleeding?»

(3 missing after 21 is replaced by «never stroke»-answer in NT3-4).

Hypertension [bpsystmn23\_nt2blm] continuous confounder (21 missing)

- Systolic blood pressure is measured three times, and the variable is the mean of the second and third measurements.

Smoking [smostat\_nt2blq1] ordinal categorical confounder (69 missing)

- Categorised into 0 «Have never smoked» 1 «Former smoker» 2 «Current smoker»

(69 missing after 10 is replaced by «never smoked»-answer in NT3-4).

Traumatic brain injury [hospheadinju\_nt2hearq1] dichotomous confounder (289 missing)

- «Have you ever been hospitalised because of a head injury?»

29 «Don't know» is merged with «No».

Body Mass Index [bmi\_nt2] continuous confounder (26 missing)

Cholesterol [sechol\_nt2blm] continuous confounder (25 missing)

Mental Health [hadstot\_nt2blq1] continuous mediator (1,175 missing)

Because of a large number of missing total scores for HADS, we include the questions from SCL-10, CON-MHI and ADI-4 in the imputation model.

1. First, the score in the mood-question in ADI-4 need to be reversed so that the variables consistently reflects that «0» is the negative answer.
2. Then non-missing total scores are found for each of the three instruments
3. To strengthen the imputation of HADS, these scores are included in the imputation model

HADS total [hadstot\_nt2blq1]

Note: «In HUNT 2 the questions on mental distress, CONOR MHI included a question close to one of the HADS items; In the last two weeks, have you felt nervous and restless. Due to limited space in the questionnaire, the corresponding question in HADS “During the last week: I feel tense or wound up” was omitted» ([HUNT Database](#)). We, therefore, have only 13 of the 14 questions in HADS.

SCL-10 [scl10tot\_nt2] continuous (502 missing)

Note: For SCL-10, we only have 9 of 10 questions. «Have you, during the last two weeks, felt bothered or distressed by anything listed below? Suddenly scared for no reason» is missing.

CON-MHI [conmhittot\_nt2] continuous (1239 missing)

For CON-MHI, we have all 7 questions.

ADI-4 [adi4tot\_nt2] continuous (798 missing)

Note: For ADI-4, we only have 3 of 4 questions. The 4th question (“During the last month, have you suffered from nervousness (felt irritable, anxious, tense or restless)?”) is probably left out because of the similarity with one of the CON-MHI-questions («In the last two weeks, have you felt: Nervous and restless?». The score for the mood-question is reversed.

We do not believe that single items missing in SCL-10 and ADI-4 will affect the imputation or analysis outcome because of the broad spectre of mental health issues already covered.

Ischemic heart disease [carinfev\_nt2blq1] dichotomous mediator (5 missing)

- «Have you ever had a heart attack?»

(5 missing after 15 is replaced by «never heart attack»-answer in NT3-4).

## Variables with no missing information

(Hearing threshold level [nt2htl54best] continuous, main exposure (0 missing))

Age [partag\_nt4blq1] continuous confounder (0 missing)

Age at participation.

Sex [sex] dichotom covariate (0 missing)

Marital status [sivilstand\_1996] dichotom covariate (0 missing)

Social isolation [live\_alone\_1996] dichotom mediator (0 missing)

Diabetes [diaev\_nt2blq1] dichotom confounder (3 missing)

- «Have you ever had diabetes?»

(3 missing after 27 is replaced by «never diabetes»-answer in NT3-4).

Education [education] ordinal confounder (0 missing)

- 0 «Unspecified/none» 1 «Primary school» 2 «Secondary school» 3 «University, < 4 years» 4 «University, >= 4 years»

(11 missing from SSB is replaced with answers from NT2).

Data from connected register Statistics Norway (SSB).

Note: We leave premorbid cognitive ability out of the analysis because of a lack of data. “Race is a poor surrogate of social constructs and even more so, if not abjectly, of biology” (Ioannidis JPA, Powe NR, Yancy C. Recalibrating the Use of Race in Medical Research. *JAMA*. 2021;325(7):623–624. doi:10.1001/jama.2021.0003). We have no suitable way of measuring air pollution (Livingston). The use of hearing aid will be assessed in another paper (hypothesis V).

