## Statistical methods

The main analysis is a logistic regression model with baseline variables from HUNT2. Missing is first handled with logical imputation, then with multiple imputation. Multiple sensitivity analyses will be run, such as complete case analysis and analysis where missing are replaced with data from other waves of the HUNT Study. Inverse probability weighting will be performed.

Registered mediators are events with unknown times of debut, but which have always occurred before they are registered. This is also the case for both incidences of dementia and hearing impairment. E.g. is the mediator «reduced mental health» believed to be worsened by hearing impairment and next leading to even more dementia. We can not know for sure the chronology of incident mental health issues and hearing impairment. Mediators will be investigated by assessing direct, indirect and total effects on the outcome.

We will model logistic regression separately for all men and women aged 70 years or older with a hearing assessment in HUNT2 and cognitive test results in HUNT4 70+. Those without a PTA and with insufficient data for a cognitive test result will be omitted from the main analysis but will be interrogated in own analysis in regards to selection bias.

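### Education level 0 pools unknown schooling with no schooling and is counted as 0 missing, so unknowns are scored as least educated and bypass the planned imputation

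*SAP*

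**What the plan says.** Under *Variables with no missing information* the SAP lists "Education [education] ordinal confounder (0 missing"). Its five codes begin "0 «Unspecified/none» 1 «Primary school" and continue through secondary school and two university levels. The data come from Statistics Norway (SSB), and a note says that "11 missing from SSB is replaced with answers from NT2".

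The general rule is in *Statistical methods*: "Missing is first handled with logical imputation, then with multiple imputation".

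Under *Variables with missing information*, traumatic brain injury is a "dichotomous confounder (289 missing"), with the remark that "29 «Don't know» is merged with «No".

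The SAP gives no count for education level 0, no split of that level into unspecified and none, and no statement of whether education enters the logistic model as a linear score or as indicators.

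**The concern.** Unspecified describes the record, not the person's schooling. Putting it at code 0 asserts that these people had less education than anyone with primary school. The zero missing count is true only because of that assertion.

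The plan already has a better rule and uses it on this same variable: the 11 people with no register value received their HUNT2 answer. Unspecified people get neither that step nor multiple imputation, and no reason is given.

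Education is in the model to remove confounding between hearing and dementia. If people of mixed schooling are placed at the bottom of the scale, the estimated education slope flattens, adjustment is incomplete, and the hearing odds ratio keeps part of the education effect. With less education going with both worse hearing and more dementia, that pushes the odds ratio away from 1.

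The planned sensitivity analyses would not show it. The complete-case analysis, the multiply imputed analysis and the analysis using other HUNT waves all act on values flagged as missing, and these values are flagged as observed in every one of them.

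**Working it through.** The SAP states no figure for the effect of this coding, so there is nothing to reproduce. The check has three parts.

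**1. How the SAP treats different kinds of unknown**

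| Unknown | Treatment in the SAP |
|---|---|
| Education, blank in register (11) | Filled from HUNT2 |
| Education, unspecified (count not given) | Scored 0, below primary school, counted as observed |
| Stroke, smoking, heart attack, diabetes: blanks | Filled only from a recorded *never* answer in a later wave; the rest left missing |
| Head injury, no answer (289) | Left missing, to be imputed |
| Head injury, does not know (29) | Set to negative, counted as observed |

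The second and fifth rows depart from the general rule.

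**2. Size of the education effect**

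All inputs are assumptions, because the document gives none of them. The simulation has 1,000,000 records. True education levels 0 to 4 have probabilities 0.002, 0.35, 0.43, 0.14 and 0.078. The education odds ratio for dementia is 0.7 per level, hearing worsens by 2.5 dB per level of lower education, and the hearing odds ratio is 1.10 per 10 dB. Age and head injury are also in the model. A random share *s* of records is then recoded to education 0.

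- Correctly coded hearing odds ratio: 1.0983, log 0.0938.
- No education adjustment at all: 1.1675, log 0.1549.
- Inflation of the log odds ratio = log(OR with miscoding) / 0.0938 − 1.

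| Unspecified share *s* | OR, linear score | Inflation | OR, indicators | Inflation |
|---|---|---|---|---|
| 0.1% | 1.0989 | 0.6% | 1.0987 | 0.4% |
| 0.5% | 1.1008 | 2.4% | 1.0992 | 0.9% |
| 1% | 1.1028 | 4.4% | 1.0997 | 1.4% |
| 2% | 1.1070 | 8.4% | 1.1005 | 2.1% |
| 5% | 1.1166 | 17.6% | 1.1026 | 4.2% |
| 10% | 1.1276 | 28.1% | 1.1058 | 7.3% |

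Share of the education adjustment lost, with a linear score at 5%: (0.1103 − 0.0938) / (0.1549 − 0.0938) = 0.0165 / 0.0611 = 27%. At 0.5% it is about 4%.

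The relative figures depend on the assumed effects. A second assumption set (education log odds ratio −0.30 per level, hearing 0.15 per 10 dB, random or age-related recoding) gives about 1%, 2.5–3.5% and 6–7% inflation at 0.5%, 2% and 5% with a linear score, and about 1% or less with categories. Both sets agree on the direction and on a larger bias under a linear score.

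**3. Size of the head-injury effect**

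Unknown answers: 29 + 289 = 318, so 29/318 = 9.1% of them are set to negative. The SAP does not give the total N. For an assumed N of 3,000 to 10,000, the 29 are 29/3,000 = 1.0% down to 29/10,000 = 0.3% of participants. With an assumed head-injury prevalence of 8% and odds ratio of 1.5, the hearing odds ratio moves from 1.0983 to at most 1.0990, even if all 29 had in truth been hospitalised.

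**The case against.** The strongest reply is that the harm depends on a number nobody outside the study has. Level 0 may hold a handful of people. The only gap in the register data that the SAP counts is the 11 blanks, and nothing in it points to 2% or 5% unspecified. This stands: the document does not support a claim that the hearing odds ratio is materially biased.

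Second, *ordinal* names a measurement scale. Smoking is called ordinal categorical, so the label does not establish a linear score, and the larger figures apply only to one. This also stands. Indicators reduce the bias but do not remove it.

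Third, if unspecified people mostly had little schooling, code 0 would be nearly right. The simulations do not test that case and the SAP does not say who these people are. The direction is therefore conditional on mixed schooling.

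Fourth, the register may supply unspecified and none as one code, in which case the two cannot be separated from the register alone. That limits the remedy, but it does not make the zero missing count correct.

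A reader might also infer that the head-injury recode weakens confounder control in the same way. It does not to any visible degree: it is disclosed with its exact count, and the effect is negligible under every assumption tried. Likewise, whether none is grouped with primary school, and whether education enters as categories, are modelling choices and not errors in the plan.

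**Conclusion.** The coding fault holds. Unknown schooling is entered as the lowest real level, the zero missing count follows from that, and the treatment is out of line with the plan's own imputation rule and with its handling of the 11 register blanks. The planned sensitivity analyses cannot detect it.

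The consequence is conditional. Given mixed schooling among the unspecified, some residual education confounding remains in the hearing odds ratio, away from 1. It is negligible below about 0.5% unspecified and could matter at several percent, mainly with a linear score. Which case applies turns on the level-0 count, the make-up of that group and the model form, none of which the SAP gives. The head-injury recode is a consistency note only.

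This is a low-cost correction worth making before analysis, not a threat to the main result on present evidence.

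**What to change.** In the education entry of the SAP:

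1. Report the number at level 0, split into unspecified and none if the register allows.
2. Set unspecified to missing, fill it from the HUNT2 education answer where one exists, and pass the remainder to the planned multiple imputation.
3. Replace the zero missing count with the number still missing after the HUNT2 fill, and move the variable to the section on variables with missing information if that number is above zero.
4. State whether education enters as a linear score or as indicators.

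If the register code cannot separate unspecified from none, use the HUNT2 answer to resolve level 0 where it is available. The SAP shows such answers only for the 11 blanks, so availability for the others has to be checked.

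Optionally, for consistency, set the 29 uncertain head-injury answers to missing and impute them with the other 289, 318 in total.

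The cost is two recodes and a few SAP lines, with no new data collection.

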## Missing

We will perform a complete case analysis to compare demographics, main exposure and main outcome, and sensitivity analysis to compare results with and without multiple imputation.

## Selection

Systematic drop-outs (dementia Vs death) with competing risk and other biases will be assessed by focusing on risk factors in mid-life. To include death causes from a national register of diagnosis is discussed, but death cause is concluded not to be very valid in the registers.

Although all participants are 70-years old or more, they may not be in their «mid-life» at baseline (HUNT2). This will be discussed.

Analysis to compare eligible and not eligible participants will be performed.

## Statistical methods

The main analysis is a logistic regression model with baseline variables from HUNT2. Missing is first handled with logical imputation, then with multiple imputation. Multiple sensitivity analyses will be run, such as complete case analysis and analysis where missing are replaced with data from other waves of the HUNT Study. Inverse probability weighting will be performed.

Registered mediators are events with unknown times of debut, but which have always occurred before they are registered. This is also the case for both incidences of dementia and hearing impairment. E.g. is the mediator «reduced mental health» believed to be worsened by hearing impairment and next leading to even more dementia. We can not know for sure the chronology of incident mental health issues and hearing impairment. Mediators will be investigated by assessing direct, indirect and total effects on the outcome.

We will model logistic regression separately for all men and women aged 70 years or older with a hearing assessment in HUNT2 and cognitive test results in HUNT4 70+. Those without a PTA and with insufficient data for a cognitive test result will be omitted from the main analysis but will be interrogated in own analysis in regards to selection bias.
